4.2. Study Efficacy Endpoints

4.2.1. Primary Efficacy Endpoint

The primary efficacy endpoint is the event rate of new PEx per subject per 28 weeks using the primary definition of new PEx comparing the lenabasum 20 mg BID and placebo cohorts. The event rate is based on the occurrence of new PEx, and the occurrence will be assessed during the treatment phase. It is defined as follows:

The primary endpoint will be calculated by the following for each treatment cohort:

Event rate of PEx (per subject-28 Weeks) for a treatment group is calculated as follows:

Total number of PEx using primary definition during the treatment period / [sum of subject treatment exposure durations in the treatment group (days) / 196]

[figure not shown]
Event rate of PEx (per subject) for a treatment group (without adjustment of treatment exposure) is calculated as follows:

Total number of PEx using primary definition during the treatment period / number of subjects in the treatment group

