5. ASSESSMENT AND DERIVATION OF EFFICACY AND BIOMARKER ENDPOINTS

5.1. Primary Efficacy Endpoint

The primary efficacy endpoint will be based on the occurrence of new PEx. The occurrence of a new PEx will be assessed throughout the active dosing period. The primary comparison of the

lenabasum 20 mg BID treatment cohort to the placebo cohort will be based on the event rate of PEx per subject per 28 weeks using the primary definition of PEx.

The event rate comparison is calculated as follows:

$$\theta = R_l / R_p$$

where R_l is the event rate of PEx per subject per 28 weeks using the primary definition of PEx for the lenabasum treatment cohort, and R_p is the event rate of PEx per subject per 28 weeks using the primary definition of PEx for the placebo group.

See [Section 4.2.1](#) for the calculation of the event rate of PEx per subject per 28 weeks.

At screening and again at Visit 1, subjects and/or their legally acceptable representative will be instructed when and how to call the site staff to report new or worsening respiratory or systemic symptoms. Subjects who experience new or worsening respiratory symptoms or have received a prescription for a new antibiotic from a physician other than a study physician should contact the site staff and return for an unscheduled Possible PEx Visit if directed to do so.

At each visit, the investigator will assess the subject for the presence of any new or worsening respiratory symptoms. The physician will assess medical history for changes from last visit, perform physical examination of the lungs and physical examination of other organs as indicated by change in medical history, and complete the AUR-Q (refer to Case Report Form).

The AUR-Q questionnaire includes Fuchs criteria (Fuchs et al, 1994) and a list of additional signs and symptoms, that may have led a physician to make a diagnosis of pulmonary exacerbation. At least 4 out of 12 Fuchs criteria are required to make a diagnosis of a new PEx by the primary definition, but not by the secondary definition.

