6.3. Sample Size and Power Considerations

The study is expected to enroll approximately 415 subjects, with ~166 subjects each in the lenabasum 20 mg BID and placebo BID cohorts and ~83 subjects in the lenabasum 5 mg BID cohort (accounting for an approximate 15% dropout rate). The study provides 80% power to detect a significant difference between the lenabasum 20 mg BID dose and placebo in the primary endpoint (PEx event rate) at a two-sided alpha of 0.05. This is based on an event rate ratio of 0.65 (a 35% event rate reduction in the lenabasum group), when the event rate in the control group is 0.80.

This also provides 90% power to detect a significant difference between lenabasum 20 mg BID and placebo BID in the secondary endpoint of time to first PEx. This is based on an estimate of the probability of an event (PEx) in the placebo group of 0.60, an estimated hazard ratio of 0.60 (risk reduction 0.40), and the probability of an event in the lenabasum group of 0.36.

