8.2. Study Treatments

8.2.1. Extent of Exposure

Treatment exposure duration will be defined as the number of days that the subject was exposed to study treatment as calculated using the formula:

$$\text{Exposure duration (days)} = \text{date of last dose} - \text{date of first dose} + 1.$$

Last dose date will be imputed using last contact date during active treatment for the subjects lost to follow up and as the date of the last visit seen, excluding safety follow-up visit, for subjects missing last dose date.

The duration of exposure will be summarized for treatment cohorts and combined lenabasum cohort. All summaries will be based on the safety population. Summary statistics will be presented for treatment exposure.

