9.2. Discontinuations, Lost to Follow-up, and Unscheduled Visits

All assessments of efficacy and safety done after discontinuation of study drug will be included in primary efficacy and safety analyses, for subjects who permanently discontinue study product, do not withdraw consent, and continue in the study.

If a subject withdraws consent, their last regularly scheduled study visit before withdrawing consent will be their last visit for efficacy and safety assessments.

If a subject is lost to follow-up, their last regularly scheduled study visit that they attended will be considered their last visit.

Efficacy assessments done at Unscheduled Visits and Possible PEx visits will be counted in efficacy analyses, only if AUQ-R at that visit indicates that the subject is having a PEx that meets primary or secondary definitions of a new PEx. Otherwise, efficacy assessments done at unscheduled visits and Possible PEx visits will be included only in listings.

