9.4. Primary Efficacy Analysis

9.4.1. Event Rate of New Pulmonary Exacerbations per Subject per 28 Weeks by Primary Definition

The primary efficacy endpoint is the event rate of new PEx per subject per 28 weeks using the primary definition (Sections [4.2.1](#) and [5.1](#)), for the comparison of lenabasum 20 mg BID cohort to the placebo cohort, in the mITT population, through Visit 8 (Week 28) which is the treatment period.

The event rate per subject per 28 weeks of new PEx will be compared between the lenabasum and placebo cohorts using a Poisson regression model with effects of treatment and log (subject treatment exposure duration), adjusting for baseline subject characteristics of site location (United States; other countries), number of new PEx requiring IV antibiotics in the previous year (1; 2; 3); FEV1 % predicted (< 70; \geq 70); and baseline CFTR-targeting medications use (Yes; No – taken concomitantly on Day 1, baseline), and based on the mITT population.

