9.4.2. Sensitivity Analyses of Primary Endpoint Analysis

The following sensitivity analyses will be performed using the same statistical method as the primary endpoint analysis, including adjusting for baseline subject characteristics of site location (United States; other countries), number of new PEx requiring IV antibiotics in the previous year (1; 2; 3); FEV1 % predicted (< 70; \geq 70); and baseline CFTR- targeting medications use (Yes; No):

- The event rate per subject per 28 weeks of PEx will be compared between the lenabasum 20 mg BID and placebo cohorts using a Poisson regression model with effects of treatment and log (subject treatment exposure duration), based on the PP population.

- The event rate per subject per 28 weeks of PEx will be compared in the lenabasum 20 mg BID and placebo cohorts using a negative binomial model with effects of treatment and log (subject treatment exposure duration), based on the mITT population. Negative binomial regression is a generalization of Poisson regression which loosens the restrictive assumption that the variance is equal to the mean made by the Poisson model.
- The event rate per subject per 28 weeks of PEx will be compared in the lenabasum 20 mg BID and placebo cohorts using a negative binomial model with effects of treatment and log (subject treatment exposure duration), based on the PP population.

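### Log exposure is written as a model effect rather than an offset, so the primary model need not estimate the per-28-week rate ratio that the plan defines

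*SAP*

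**What the plan says.** Section 4.2.1 defines each cohort's rate as the number of exacerbations divided by "sum of subject treatment exposure durations in the treatment group (days) / 196". Section 5.1 sets theta as the lenabasum rate over the placebo rate, where the numerator "is the event rate of PEx per subject per 28 weeks using the primary definition of PEx for the lenabasum treatment cohort". Section 6.2 tests theta = 1.

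Section 9.4.1 compares the cohorts with a "Poisson regression model with effects of treatment and log (subject treatment exposure duration"), adjusted for four baseline characteristics. Section 9.4.2 repeats the construction in all three sensitivity models, for example "using a negative binomial model with effects of treatment and log (subject treatment exposure duration), based on the mITT population". Section 9.5.1 applies the primary method to the secondary rate endpoints. The SAP nowhere uses the word offset or fixes a coefficient at 1.

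Two further rules bear on the exposure term. Section 8.2.1 states: "Treatment exposure duration will be defined as the number of days that the subject was exposed to study treatment", calculated as last dose minus first dose plus one day. Section 9.2 states: "All assessments of efficacy and safety done after discontinuation of study drug will be included in primary efficacy and safety analyses", for subjects who stop drug, do not withdraw consent and remain in the study. Section 5.1.1 accepts a new exacerbation up to Visit 8 or discontinuation from the study. Section 13, in contrast, describes the analyses as generally on-treatment.

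**The concern.** A rate per exposure time comes from a log-linear count model when log exposure enters with its coefficient fixed at 1. Listed as an effect beside treatment, it is by ordinary usage a regressor with an estimated slope. The treatment coefficient then compares mean counts at equal exposure. Exposure arises after randomisation and may differ between arms, so this is not in general the declared theta.

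The primary test gates the whole hierarchy (Section 9.3), and Section 2 bars sponsor changes after signature. If the wording stays as it is, two programmers could each follow the SAP faithfully and report different primary estimates, occasionally on opposite sides of significance.

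**Working it through.** **1. The plan's own power figure.** Inputs from Section 6.3: 166 per arm, 15% dropout, control rate 0.80, ratio 0.65, "two-sided alpha of 0.05". The control rate is taken as per 28 weeks.

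- n = 166 × 0.85 ≈ 141 per arm; active rate = 0.80 × 0.65 = 0.52.
- SE of the log ratio = √[1/(141 × 0.80) + 1/(141 × 0.52)] = 0.150.
- Power = Φ(0.431/0.150 − 1.96) = Φ(0.91) ≈ 81.9%, which reproduces the stated 80% to within 2 points.
- Simulated with 166 randomised per arm and 15% uninformative dropout: 85.2% with the offset, 85.3% with the free slope. The choice does not affect power.

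**2. What each form estimates.** Leave out the baseline covariates. Let Y be an arm's total events, d a subject's exposure and b the fitted slope. The Poisson score equations give

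exp(treatment coefficient) = [Y_L / Σ_L d^b] ÷ [Y_P / Σ_P d^b].

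With b = 1 (the offset) this is exactly the Section 4.2.1 ratio. With b = 0 it is the ratio of events per subject, the version that Section 4.2.1 labels as not adjusted for exposure. A free slope lets the data choose b. The forms agree when b is near 1, or when the exposure distributions match so that the sums cancel.

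**3. Size of the difference, by hand.** Assume stopping times uniform over 5% to 100% of the 28 weeks. The average of d is then 0.525 among stoppers, and the average of d^0.6 is (1 − 0.05^1.6)/(1.6 × 0.95) = 0.652. With 10% (placebo) and 20% (20 mg) stopping:

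- b = 1: mean exposures 1 − 0.10 × 0.475 = 0.9525 and 1 − 0.20 × 0.475 = 0.905; placebo/active = 1.0525.
- b = 0.6: 1 − 0.10 × 0.348 = 0.965 and 1 − 0.20 × 0.348 = 0.930; placebo/active = 1.037.
- Free slope relative to offset: 1.037/1.0525 ≈ 0.986, a shift of about 1.4%.

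**4. Simulation.** 166 per arm, control rate 0.80, 1,500 runs per row, no baseline covariates. The stopping patterns and frailty are assumptions; the SAP gives only the overall 15%.

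| Pattern | Placebo / 20 mg stopping | True ratio | Mean slope | Offset | Free slope |
|---|---|---|---|---|---|
| Leave study, uninformative | 15% / 15% | 0.65 | 1.10 | 0.649 | 0.648 |
| Leave study, uninformative | 5% / 25% | 0.65 | 1.11 | 0.646 | 0.648 |
| Leave study, frailty-linked (variance 0.5) | 15% / 15% | 0.65 | 0.60 | 0.650 | 0.650 |
| Leave study, frailty-linked | 10% / 20% | 0.65 | 0.60 | 0.629 | 0.619 |
| Leave study, frailty-linked | 5% / 25% | 1.00 | 0.57 | 0.952 | 0.920 |
| Stop drug, stay, events counted | 15% / 15% | 1.00 | 0.02 | 0.996 | 0.996 |
| Stop drug, stay, events counted | 10% / 20% | 0.65 | 0.03 | 0.681 | 0.648 |
| Stop drug, stay, events counted | 5% / 25% | 1.00 | 0.02 | 1.101 | 0.995 |

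In a harsher case (frailty variance 1.0, dropout hazard rising with frailty to the power 1.5, 10% / 25%, no effect) the ratio was about 0.90 with the offset and 0.86 with the free slope. False rejection was about 18% and 21% to 25% across runs.

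**5. Why an offset alone is not enough.** The last three rows follow Sections 8.2.1 and 9.2: events count after drug is stopped, but exposure does not. Suppose all stoppers stay, event rates are constant, and stoppers stop on average at fraction m of the 28 weeks. The offset then multiplies the true ratio by

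[1 − p_P(1 − m)] / [1 − p_L(1 − m)].

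For 10% versus 25%: m = 0.5 gives 0.95/0.875 = 1.09, and m = 0.4 gives 0.94/0.85 = 1.11. Simulations under no effect gave 1.09 to 1.10 with 10% to 11% rejection for the offset, against 1.00 with 4% to 5% for the free slope.

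**The case against.** The strongest reply is that the wording is shorthand. Section 9.4.1 says that a rate per 28 weeks is being compared, refers back to Sections 4.2.1 and 5.1, and names log exposure apart from the baseline adjusters. A logged exposure term in a log-link count model is what an offset looks like. That reading is plausible, but the text does not fix it.

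Several stronger conclusions might be inferred, and the SAP does not support them:

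- *The primary model cannot estimate theta.* It does when counts are proportional to exposure or exposure is balanced, even with a slope far from 1 (rows 3 and 6).
- *The free slope favours the arm with more dropout.* That holds in the frailty rows. When subjects stop drug but stay, the free slope is close to the truth and the offset is biased against the arm with more stopping.
- *The false-rejection rates are caused by this wording.* Most remains with the offset. With frailty variance 1.0 and uninformative dropout, both forms reject about 13.5%, which is overdispersion; the negative binomial analysis in Section 9.4.2 addresses that. Only about 4 to 7 points in the harshest case belong here.
- *Adding an offset has no downside.* Step 5 shows otherwise.

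**Conclusion.** The point holds as a specification defect in the primary model. Followed literally, Sections 9.4.1 and 9.4.2 (and 9.5.1 by reference) do not in general deliver the ratio that Sections 4.2.1, 5.1 and 6.2 define. The practical size is modest and conditional: nil under balanced or uninformative dropout, and about 0.01 to 0.04 in the ratio under assumed differential, frailty-linked dropout. It is larger where off-drug events count against on-drug exposure (0.681 versus 0.648 at 10% / 20%, true ratio 0.65). At a true ratio of 0.75, the two readings disagreed on significance in about 4% to 6% of simulated trials under frailty-linked dropout, and in 17% under the off-drug pattern. All of this rests on stopping patterns that the SAP does not give. Stated power is unaffected.

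The mismatch between the event-counting period and the exposure period belongs to the same defect, because it determines whether a slope of 1 is appropriate.

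**What to change.** Make two changes together, before unblinding.

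1. In Sections 9.4.1 and 9.4.2, state that log(duration/196) enters as an offset with its coefficient fixed at 1, and remove it from the list of effects. Section 9.5.1 follows by reference.
2. Define duration, for the rate in Section 4.2.1 and for the models, over the same period in which exacerbations are counted, and reconcile Sections 5.1.1, 8.2.1, 9.2 and 13. If events count to Visit 8 or study discontinuation, the denominator should run to that date. If the analysis is on-treatment, events after the end of the exposure period should leave the numerator.

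The cost is a few sentences, one programming option and a decision on the counting period; the sample size does not change. The first change should not be adopted without the second, because the offset alone carries the mismatch into the primary estimate. Neither change cures informative dropout, which remains a separate limitation.

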4.1.4. Study Population and Background Treatment for CF

The study population is males and females with CF \geq 12 years of age with FEV1 \geq 40% predicted and $<$ 100% predicted at least once within 12 months before Screening. Subjects must have 2 to 3 new PEx treated with IV antibiotic therapy within 12 months before Screening or, as an alternative, 1 new PEx treated with IV antibiotics and at least 1 PEx treated with oral antibiotics within 12 months before Screening.

Subjects should be considered stable and on stable medication for treatment of CF prior to Visit 1. For example, subjects are allowed use of prophylactic antibiotics and CFTR-modulating medications if they are on stable doses within 28 days of Visit 1. A subject with an increase in dose or initiation of any new chronic therapy for CF within 28 days of Visit 1 is not eligible for enrollment. Changes in treatment of CF after study start are allowed when those changes are in the subject's best medical interest, as assessed by the treating physician. Sensitivity analyses will be performed to assess potential impact of treatment at Baseline with drugs that might reduce rate of PEx, including concomitant CFTR-targeting medications, azithromycin, prophylactic antibiotics, and dornase alfa on the primary and first secondary efficacy outcome.

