4.1.9. Randomization, Stratification Factors, Treatment Cohorts, and Dosing

Before dosing on Visit 1 (Day 1), eligible subjects will be randomly assigned using an Interactive Web-based Response Technology system to one of three treatment cohorts, based on a randomization schedule prepared by an independent biostatistician who was not involved in the day-to-day conduct of the study. The randomization will be stratified by number of previous new PEx requiring IV antibiotics in the previous year (“1 vs 2 or 3”; however, this changed approximately midway of study to “1 or 2 vs 3”, See [Section 13](#)), FEV1 % predicted at baseline (< 70; ≥ 70) and location of site (United States; Non-United States).

Subjects will be randomized in a 2:1:2 ratio to 1 of 3 treatment cohorts:

- Cohort 1: Lenabasum 20 mg BID, n = 166

- Cohort 2: Lenabasum 5 mg BID, n = 83
- Cohort 3: Placebo BID, n = 166

Twice per day dosing consists two doses each day with at least 8 hours between doses. Subjects will self-administer study product, which will be taken by the oral route and with no requirement as to fed or fasting state. Phase 1 data showed little impact of the fed-state on exposure to lenabasum, and subjects in all Phase 2 studies to date have taken lenabasum without regard to fed state.

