5.1.1. Primary Definition of New Pulmonary Exacerbation

The derivation for new PEx by the primary definition is provided below. The rules for defining new antibiotics used for new PEx, including the start and stop days, are also provided below.

Primary definition of new PEx:

- Physician diagnosis of PEx
- Prescription of new antibiotics for PEx
- Start date of new antibiotics for PEx is > 28 days after the stop date of any antibiotics given for any previous PEx. The physician does not need to determine if there is > 28 days from last use of antibiotics to the new antibiotics for PEx analysis purposes. The > 28-day gap will be determined centrally
- A new PEx is not defined by the number of antibiotics prescribed or the order or route of administration of the antibiotics (oral or IV) for that new PEx
- ≥ 4 out of 12 Fuchs criteria are met

New antibiotics for PEx

- Must be given for PEx

- Must be administered by oral or IV route
- Start date is day the physician prescribes that the subject should take this antibiotic treatment for a PEx
- Stop date is the last day the physician prescribes that the subject should take this antibiotic treatment for a PEx
- Start day > Day 1
- Start day \leq Day of Visit 8 or discontinuation from the study
- Regularly given prophylactic inhaled, oral, or IV antibiotics do not count as new antibiotics unless the dose is increased or given early for a PEx

Start day of a new PEx:

The first day that the physician prescribes that the subject should take any new antibiotic treatment for that new PEx

Stop day of a new PEx:

The last day that the physician prescribes that the subject should take any new antibiotic treatment for that new PEx or day of discontinuation from the study, whichever is sooner

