7.3. CF Medical History

CF medical history data will be captured at Screening visit. Details of the CF medical history will be summarized for the safety populations in a table and presented in a listing.

The following CF medical history will be summarized for the mITT:

- Age at diagnosis (years)
- Method of diagnosis – sweat test
- CFTR genotype (mutation allele #1, mutation allele #2)
- Previous infections (*Aspergillus*, *Burkholderia cepacia*, *Mycobacterium abscessus*)
- Primary pathogenic species present (yes; no) in sputum cultures at Baseline (*Pseudomonas aeruginosa*, *Staphylococcus aureus*, *Aspergillus fumigatus*, *B. cepacia*, *M. abscessus*, *Streptococcus pneumoniae*)
- Lowest FEV1 % predicted in the last year
- Highest FEV1 % predicted in the last year
- Hemoptysis in the last year
- Number of acute PEx in the last year
- Number of acute PEx treated with IV antibiotics in the last year
- Time since last PEx requiring IV antibiotics (days), calculated as:
First dose date of study drug – date of the last PEx requiring IV antibiotics + 1
- Antibiotic(s) used prophylactically
- Other organ involvement (Pancreatic insufficiency, diabetes, sinusitis, nasal polyps)

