9.5.3. Time to New Pulmonary Exacerbations

Time to first new PEx (days) for subjects with a new PEx is calculated as:

Date physician initiates antibiotic(s) for first new PEx – first dose date of study drug + 1

Time to first PEx for subjects without a new PEx (days event free) is calculated as:

Date of last dose of study product during the 28-Week treatment period – first dose date of study drug + 1

For time to first new PEx analyses, a Cox-proportional hazards (regression) model will be used for comparing the covariate-adjusted difference in event-time distributions between the active and placebo cohorts. Covariates in the model will include site location (United States; Non-United States), number of new PEx requiring IV antibiotics in the previous year (1; 2; 3); FEV1 % predicted (< 70; ≥ 70); and baseline CFTR-targeting medications use (Yes; No). Hazard ratios will be provided.

A life-table method will be used to estimate survival probabilities in 14-day intervals between Day 1 to 182 plus a final interval of ≥ 183 days. Subjects at risk, number of PEx, number of

censored in each time interval and overall, survival probability in each time interval, Kaplan-Meier estimated first quartile, median and third quartile of time, hazard ratios (lenabasum/placebo) and associated 95% CI, and log-rank p-values will be provided.

The time to PEx will be evaluated using a Kaplan Meier method. The homogeneity of event time distribution will be tested between each and overall active treatment cohorts as compared to placebo using a log-rank or a weighted log-rank test (Fleming-Harrington) in case of non-parallel curves across groups.

[figure not shown]

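### The exacerbation models adjust for IV-treated history only, although the endpoint counts oral- and IV-treated events; adding the collected total count is a small, cheap gain

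*SAP*

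**What the plan says.** - **Entry (4.1.4).** There are two routes: "Subjects must have 2 to 3 new PEx treated with IV antibiotic therapy within 12 months before Screening", or "1 new PEx treated with IV antibiotics and at least 1 PEx treated with oral antibiotics within 12 months before Screening". Neither states an upper limit on oral-treated events.
- **Endpoint (5.1.1).** The antibiotic "Must be administered by oral or IV route", and "A new PEx is not defined by the number of antibiotics prescribed or the order or route of administration of the antibiotics (oral or IV"). Oral- and IV-treated events count alike.
- **Randomisation (4.1.9).** "The randomization will be stratified by number of previous new PEx requiring IV antibiotics in the previous year", together with FEV1 % predicted and site location.
- **Models.** The primary Poisson model (9.4.1) adjusts for "number of new PEx requiring IV antibiotics in the previous year (1; 2; 3"). The Poisson and negative binomial sensitivity analyses (9.4.2), the other rate endpoints (9.5.1) and the Cox model (9.5.3) carry the same history term.
- **Collected history (7.3).** "Number of acute PEx in the last year" is listed for descriptive summary in the mITT population, as is the IV-treated count.

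**The concern.** The endpoint counts all treated exacerbations, but the only history term counts a subset of past ones. A subject with one IV-treated and one oral-treated event sits at the same covariate value as a subject with one IV-treated and four oral-treated events, and the two would not be expected to have the same on-study rate. A count closer in kind to the endpoint is already collected.

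Two things are at stake, both modest. Between-subject variation that could be explained stays in the residual. A chance imbalance in oral-treated history would go unadjusted in the primary comparison, on which the testing hierarchy of 9.3 depends.

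**Working it through.** **1. What each IV level can contain under 4.1.4**

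| IV-treated PEx | Minimum oral-treated | Minimum total | Stated maximum total |
|---|---|---|---|
| 1 | 1 | 2 | none |
| 2 | 0 | 2 | none |
| 3 | 0 | 3 | none |

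The mixing occurs at all three levels, and levels 1 and 2 share the same minimum.

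**2. The plan's own power figure (6.3)**

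Inputs: control rate 0.80, rate ratio 0.65 (active rate 0.80 × 0.65 = 0.52), two-sided alpha 0.05, and 166 per arm with 15% dropout, so 166 × 0.85 ≈ 141.

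Power = Φ(|ln 0.65| / √((1/0.80 + 1/0.52)/n) − 1.96)

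- n = 141: 0.4308 / √(3.173/141) = 0.4308/0.1500 = 2.87; Φ(0.91) = 81.9%.
- n = 166: 0.4308/0.1383 = 3.12; Φ(1.16) = 87.6%.

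The stated 80% reproduces with 141 per arm. It assumes pure Poisson variation and no covariates, so it does not depend on this point.

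**3. Simulation with an explicit link to total history**

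The SAP gives neither the distribution of oral-treated PEx nor their relation to the on-study rate, so these are assumptions:
- IV levels 1/2/3 in proportions 40/40/20%.
- Extra oral PEx Poisson with mean 1 or 2.
- On-study rate proportional to (total PEx)^b.
- 166 per arm, 15% dropout, 1,500 runs per scenario.
- Unscaled Poisson model with an exposure offset and the IV count as categories; other covariates left out.

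The SD is the empirical SD of the log rate ratio at a true ratio of 0.65. The variance change is the squared ratio of SDs minus 1. Arrows run from IV count only to IV count plus log total.

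| b | Extra oral mean | SD | Variance change | Type I error, % | Power, % |
|---|---|---|---|---|---|
| 0.5 | 1 | 0.1440 → 0.1443 | +0.4% | 6.0 → 5.6 | 84.7 → 84.7 |
| 0.5 | 2 | 0.1486 → 0.1485 | −0.1% | 3.4 → 3.5 | 85.1 → 84.9 |
| 1.0 | 1 | 0.1489 → 0.1456 | −4.4% | 6.2 → 5.5 | 85.3 → 86.2 |
| 1.0 | 2 | 0.1514 → 0.1473 | −5.3% | 5.1 → 4.1 | 83.7 → 83.9 |
| 1.5 | 1 | 0.1587 → 0.1491 | −11.7% | 6.3 → 4.2 | 83.7 → 85.8 |
| 1.5 | 2 | 0.1579 → 0.1465 | −13.9% | 7.4 → 4.7 | 83.5 → 84.8 |

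The Monte Carlo standard error is about 0.6 points for type I error and 0.9 for power. The mean estimated ratio was 0.99 to 1.01 under the null and 0.65 under the alternative with either model, so there is no bias. Here total history is the only source of extra variation, which favours the added covariate.

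**4. Simulation with a latent subject rate**

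Assumptions: gamma-distributed annual rates with mean 2 to 3 and squared CV 0.5 to 0.8; 35 to 50% of PEx IV-treated; the 4.1.4 entry rule; 28-week mean 0.80. Ranges are over repeated sets of runs.
- Expected 28-week rate within IV level 1: 0.48–0.61 at a total of 2, and 0.89–1.07 at a total of 5.
- Expected rate between levels: 0.67–0.76 at level 1 against 0.78–0.84 at level 2.
- Variance of the log rate ratio with log total added: 1 to 8% lower.
- Power: −1 to +2 points.
- Type I error of the unscaled Poisson model: 7.2–9.0% falls to 6.3–7.8%.
- If IV treatment tracks severity, the gain nearly vanishes.

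**5. Reconciling the two**

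In step 4 the rate at a total of 5 is between 0.89/0.61 = 1.46 and 1.07/0.48 = 2.23 times the rate at a total of 2. The counts themselves differ by 5/2 = 2.5. The implied b lies between ln 1.46/ln 2.5 = 0.41 and ln 2.23/ln 2.5 = 0.87. The b = 1.5 rows lie outside that range, so 1 to 8% is the more credible size. An 8% lower variance is a 1 − √0.92 = 4% smaller standard error.

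**The case against.** The case against is strong on framing.

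- **The IV count is the stratification variable, so adjusting for it is correct.** This stands. Nothing in the SAP says the models should use the total, and there is no contradiction. It does not rule out a further covariate: Section 13 adds baseline CFTR-medication use, which is not a stratification factor in 4.1.9.
- **The negative binomial analysis in 9.4.2 already deals with overdispersion.** This stands in part. It allows for unexplained variation but uses the same IV-only history term, and it is a sensitivity analysis.
- **The reported precision would hardly change.** This stands. 9.4.1 states no dispersion scaling, so the model standard error at a ratio of 0.65 stays near 0.145 either way. The gain shows in the actual spread of the estimate and in type I error.
- **The historical count is not the endpoint.** This stands. The item in 7.3 applies neither the Fuchs criteria nor the rule of more than 28 days between antibiotic courses, and the strength of its link to the on-study rate is assumed.
- **The text may be incomplete.** 4.1.4 summarises eligibility, and the protocol could cap oral-treated events. 4.1.4, 4.1.11 and 4.1.12 also promise sensitivity analyses that the visible 9.4.2 does not list. The statement is therefore limited to the models that can be seen.

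A reader might infer that level 1 alone is badly formed, or that it holds low-frequency subjects. Oral-treated events are uncapped at every level, and every eligible subject has at least two PEx. A reader might also infer that the Cox results lose precision. Leaving a balanced prognostic covariate out of a Cox model mainly attenuates the hazard ratio; it does not mainly widen its standard error.

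**Conclusion.** The point holds as a minor improvement. The history term covers only part of what the endpoint counts, each IV level mixes total histories, and a closer predictor is collected but enters no visible model.

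Under the assumed distributions, adding it lowers the variance of the log rate ratio by roughly 1 to 8% and changes power by about 0 to 2 points. It slightly reduces the type I error excess of the unscaled Poisson model without removing it. These figures rest wholly on assumed PEx distributions and an assumed link to on-study rate. The gain could be close to nil.

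The documents do not support a reading that the primary analysis is biased or wrong, that the total count is ignored altogether (7.3 summarises it, so an imbalance between arms would be visible), or that this covariate would cure overdispersion.

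**What to change.** Before unblinding, add the log of the total number of PEx in the last year, as collected under 7.3, as a baseline covariate in 9.4.1, 9.4.2, 9.5.1 and 9.5.3. Keep the IV-count term. Record the addition in Section 13 beside the CFTR-medication covariate. The log is defined for every eligible subject, since the minimum total is 2; state a rule for missing or out-of-range counts. If the sponsor prefers to leave the primary model alone, prespecify this as a sensitivity model for the primary and first secondary endpoints.

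The same edit should settle the coding of the IV count, which 9.4.1 lists as three values and Section 13 calls continuous. That is a separate matter.

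The cost is one degree of freedom, some recall error in a history-reported count, and a few lines of text. Section 2 rules out sponsor changes after signature, so the addition has to be made before then.
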